6.3 Exclusion Criteria

Deviations from exclusion criteria are not allowed because they can potentially jeopardize the scientific integrity of the study, regulatory acceptability or participant safety. Therefore, adherence to the criteria as specified in the protocol is essential.

Participants will be excluded from the study if any of the following criteria are met:

- 1. Clearly defined etiology for pruritus other than atopic dermatitis. These include but are not limited to urticaria, psoriasis or other non-atopic dermatologic conditions, hepatic or renal disease, psychogenic pruritus, drug reaction, untreated hyperthyroidism, parasite presence and presence of acute infection either systemically or in the AD lesions.
- 2. Presence of any acute condition which may risk inducing an atopic dermatitis flare during the course of the study, such as impetigo or active herpes simplex infection.
- 3. Treatment with systemic corticosteroids within 4 weeks prior to randomization.
- 4. Treatment with Class III or higher potency topical corticosteroids or any topical antipruritic therapies (other than stable doses of low- or mid-potency topical corticosteroids or bland emollients) within 4 weeks prior to randomization.
- 5. Treatment with systemic therapies with recognized anti-pruritic (e.g. tricyclic antidepressants, sedatives, tranquilizers, gabapentin, marijuana or other cannabinoids, opioid receptor agonists/antagonists) or pruritic (e.g. opioids, angiotensin-converting enzyme inhibitors, cocaine, antimalarials) properties within 4 weeks prior to randomization.
 - a. Stable doses of H1 antihistamines will be permitted. Subjects must be willing to continue these at the same doses and frequencies throughout the study inclusive of the follow-up period.
- 6. Any clinically significant changes in type, dose, or frequency of bland emollients, low- or mid-potency corticosteroids, and/or oral H1 antihistamines throughout the study from screening to follow-up.
- 7. Treatment with systemic immunosuppressive/ immunomodulatory therapies within 4 weeks prior to randomization (including but not limited to phosphodiesterase-4 inhibitors, cyclosporine, mycophenolate-mofetil, methotrexate, azathioprine, interferongamma, or phototherapy).
- 8. Treatment with biologic therapies within 12 weeks or 5 half-lives prior to randomization, whichever is longer.
- 9. Use of an indoor tanning facility within 4 weeks prior to randomization.

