7.3 Study Withdrawal and Withdrawal from Investigational Product and Stopping Criteria

A participant may withdraw from the study at any time at his/her own request, or may be withdrawn at any time at the discretion of the Investigator.

Reasons for withdrawal (participants who refuse to complete any remaining study visits) or discontinuation (participants who prematurely stop the application) at any time during the study may include, but are not limited, to the following:

- For safety reasons, either at the discretion of the Investigator or at the participant's request
- For protocol violations at the discretion of AOBiome
- Withdrawal of consent by the Subject
- Lost to follow-up
- Due to use of concomitant therapy that could interfere with the results of the study (the Investigator will report all such information through the CRF and decide, in accordance with AOBiome, whether the participant is to be withdrawn).

The reason for participant study withdrawal will be recorded in the electronic Case Report Form (eCRF). Data from participants withdrawing from the study will be considered evaluable up to the point at which they are withdrawn using the same criteria for evaluability as for participants who complete the study.

Study stopping rules will be implemented to stop the study for safety review in the event that:

- 1 subject reports death, or
- >2 subjects report an SAE, or
- >4 subjects experience grade 3 AEs of a similar type, or
- >6 subjects experience grade 2 AEs of a similar type

when the reported SAEs or AEs are considered possibly, probably, definitely or related to the investigational product.

Atopic Dermatitis is an active disease with known seasonal and personal histories of flares and exacerbations of the patient's underlying disease state. This includes personal histories of worsening itch and itch-scratch cycles, which can lead to localized infection and localized cellulitis. A subject's known and collected clinical history should be considered by the principal investigator when determining relationship of event to the investigational product.

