8.14 Rescue Medications

8.14.1 Rescue Medication Permitted During the Study

Over the course of the study, the Investigator will monitor and evaluate subject's condition and determine whether rescue therapy may be necessary. The use of medications to treat a subject's atopic dermatitis during the study will be permitted if a medical professional determines that it becomes medically necessary. Such rescue treatment should not exceed 7 days per month for the duration of the trial (screening, washout, treatment, and follow-up), e.g., no more than 3 days total during the 2 week washout period, no more than 7 days total during the 4 week follow-up period. If a subject requires treatment for more than 7 days per month or requires systemic therapy, they may be discontinued from the study. Medications permitted are listed in Table 8.1.

In the event of an atopic dermatitis or pruritus exacerbation in between visits, subjects should contact study staff as soon as they are able. Subjects should seek approval on the use of rescue medications. In the event that the subject did not notify the study staff, every effort should be made by the subject to contact the PI or study staff as soon as feasible. The details of the medication should be recorded in the eDiary and transferred to the CRF. Details recorded should include medication name, date of administration, dosage, and number of applications.

Table 8.1 Permitted Rescue Medication

Class 4 – Mid-strength			
Clocortolone pivalate (0.1%)	Cloderm® Cream		
Mometasone furoate (0.1%)	Elocon® Cream		
Triamcinolone acetonide (0.1%)	Aristocort® A Cream, Kenalog® Ointment		
Betamethasone valerate (0.1%)	Valisone Ointment		
Fluocinolone acetonide (0.025%)	Synalar® Ointment		
Class 5 – Lower Mid-strength			
Fluticasone propionate (0.05%)	Cutivate® Cream/Cutivate Lotion		
Prednicarbate (0.1%)	Dermatop® Cream		
Hydrocortisone probutate (0.1%)	Pandel® Cream		
Triamcinolone acetonide (0.1%)	Aristocort A Cream, Kenalog Lotion		
Fluocinolone acetonide (0.025%)	Synalar Cream		
Class 6 – Mild			
Alclometasone dipropionate (0.05%)	Aclovate® Cream/Ointment		
Desonide (0.05%)	Verdeso™ Foam, Desonate Gel™		
Triamcinolone acetonide (0.025%)	Aristocort A Cream, Kenalog Lotion		
Hydrocortisone butyrate (0.1%)	Locoid Cream/Ointment		
Fluocinolone acetonide (0.01%)	Derma-Smoothe/FS® Scalp Oil, Synalar Topical Solution		
Class 7 – Least potent			
Hydrocortisone (2%/2.5%)	Nutracort® Lotion, Synacort Cream		

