7.2.5 Per-Protocol (PP) Population

The PP population includes all subjects in the mITT population without any major protocol deviations that may have an impact on the efficacy assessments, who complete their Week 4 visit, and who administer at least 50% of investigational product (IP). Subjects will be grouped as treated.

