PP population excludes subjects with any major protocol deviation that may impact efficacy and safety analyses, including those with any confounding events or those over the rescue medication use limits but includes data for subjects below rescue medication use limits. Rescue medication

STATISTICAL ANALYSIS PLAN

Version 3.0 12-Jan-22

use below the allowed limit per protocol are considered minor protocol deviations, are considered non-confounding, and is included in the PP population.

The following events are confounding:

- Change in stable use of oral H1 antihistamines (e.g., change in type, dose, and frequency of medication)
- Change in stable use of bland emollients (e.g., change in type, dose, and frequency of treatment)
- Use of excluded medications during study
- Use of rescue medications over the allowed limit per protocol (over 3 rescue medication days during the 2-week washout period, over 7 rescue medication days during the 4-week treatment, and over 7 rescue medication days during the 4-week follow-up)

In the PP sub-analysis, all subject data over the rescue medication limits per the PP primary analysis will be excluded, but subject data below the rescue medication limits will be included up to the date or week that the first rescue medication is taken.

Hypothesis tests for the primary efficacy endpoint will be performed using a Dunnett Testing Method, applying pairwise comparisons of each respective B244 dose group to vehicle using a one-sided familywise error rate of 0.10. Section 7.4.2 provides further details. No additional adjustments will be made for multiple testing. As such, p-values from analysis of secondary and exploratory efficacy analyses must be interpreted in an exploratory fashion.

Supportive analyses may be performed for all efficacy analyses combining the B244 dose groups in comparison against vehicle and comparison of the B244 groups to one another.

Furthermore, stratified analyses will be performed by presenting descriptive statistics by age group, race, gender, IGA at Baseline (2 or 3), EASI at baseline (≤ 10 or >10), BSA range at Baseline (10 to 20%, >20 to 30%, >30 to 40%), rescue treatment used at Baseline (Yes, No), and rescue medication used while on treatment (Yes/No).

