[2] Each time interval is normalized as a rate where (# Rescue Medication Days) = [(# Days Rescue Medications Used in Interval) / (# Actual Days in Interval)] * (# Expected Days in Interval).

[3] Rescue medication thresholds: ≤ 3 days in washout period (baseline), ≤ 7 days during Weeks 1 - 4, ≤ 7 days during Weeks 5 - 8.

Source: SDTM.XXXX or ADaM.XXXX

PROGRAM NAME: XXXXXXXXXX

DATE: HH:MM/DDMMMYYYY

Programming Notes:

• More than Threshold column should be populated for Study Periods: Baseline, Weeks 1 – 4, and Weeks 5 – 8.

Listing 16.2.14 Medical History (Safety Population)

| Subject ID | Treatment | Preferred Term [1] | MH # | Start Date | End Date/Ongoing | Current Treatment | CM # |
|---------------|--|----------------------------------|-----------|------------|-----------------------|-------------------|------|
| XXXXXX | N/A, B244 O.D. 5.0, B244 O.D. 20.0, Vehicle | xxxxxxx/ xxxxxxxx | XXX | DDMMMYYYY | DDMMMYYYY, Ongoing | Yes, No | XXX |
| [1] MedDRA Di | ictionary version XX.X w | vas used to code medical history | v events. | | | | |

Source: SDTM.XXXX or ADaM.XXXX PROGRAM NAME: XXXXXXXXXX

DATE: HH:MM/DDMMMYYYY

Listing 16.2.15.1 COVID-19 Test Results (Safety Population)

| Subject ID | Treatment | Test Date | COVID-19 Test | Test Type [1] | Result Type [2] | Result | Medically Confirmed |
|-------------------|--|----------------------------|--|-----------------|-----------------|-----------------------|------------------------|
| XXXXXX | N/A, B244 O.D. 5.0, B244 O.D. 20.0, Vehicle | DDMMMYYYY | Antibody, Viral, Other (specify) | Antigen, RNA | IgM, IgG | Positive, Negative | Yes, No |
| [1] Test type she | ould only be populated fo | r the Viral COVID-19 test. | | | | | |
| [2] Result type s | should only be populated | for the Antibody COVID-1 | 19 test. | | | | |
| Source: SDTM. | XXXX or ADaM.XXXX | | | | | | |
| PROGRAM NA | ME: XXXXXXXXXX | | | | | DATE: H | H:MM/DDMMMYYYY |

Listing 16.2.15.2 COVID-19 Missed Assessments (Safety Population)

| Subject ID | Treatment | Affected Visit | Assessments Not Done | Reason Not Done |
|------------|-----------------|----------------|----------------------------|--|
| XXXXXX | N/A, | Screening, | eDiary Review, | Site Closure, |
| | B244 O.D. 5.0, | Baseline, | IP Compliance, | Subject Decision (specify), |
| | B244 O.D. 20.0, | Week 2, | IP Dispensation, | Subject Decision – Over 60, |
| | Vehicle | Week 4, | Application of Study Drug, | Subject Decision – Underlying Health Issues, |

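### One per-protocol set for all weeks can drop subjects for events after Visit 4, so the supportive Week 4 analysis may be selected on outcomes that arise after its endpoint is measured

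*SAP*

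**What the plan says.** SAP 7.4 runs all efficacy analyses on mITT and PP. It describes PP as leaving out subjects with major deviations, "including those with any confounding events or those over the rescue medication use limits". Four kinds of event are listed as confounding:

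- a change in stable H1 antihistamine use;
- a change in stable emollient use;
- "Use of excluded medications during study";
- rescue use beyond the limit in washout, in treatment, "and over 7 rescue medication days during the 4-week follow-up".

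The follow-up limit comes from Protocol 8.14.1 ("no more than 7 days total during the 4 week follow-up period"). SAP Listing 16.2.13.3 flags it separately ("≤ 7 days during Weeks 5 - 8"), so a subject with no rescue on treatment can still breach it.

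The antihistamine and emollient items carry no dates. That they reach into follow-up is an inference from Protocol 6.3, which bars clinically significant changes in these therapies "throughout the study from screening to follow-up", and from Protocol 8.13.1.

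SAP 7.2.5 gives the formal definition: mITT subjects "without any major protocol deviations that may have an impact on the efficacy assessments", with a completed Week 4 visit and at least half of the product used. SAP 7.3.2 says that major deviations may lead to removal from PP at the sponsor's discretion, after a review before unblinding. None of these sections sets a time limit. SAP 7.2.6 makes mITT definitive and PP supportive.

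**The concern.** A PP analysis of Week 4 should show the effect in subjects who kept to the plan while the Week 4 endpoint was accruing. What happens in Weeks 5 to 8 is the course of the disease after study drug has ended, and Protocol 7.3 notes that "Atopic Dermatitis is an active disease with known seasonal and personal histories of flares and exacerbations". Follow-up rescue may plausibly track residual itch at Week 4, or relapse after withdrawal, and so may differ by arm.

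Take a subject with 28 clean days on drug, a complete Week 4 diary and a flare starting on Day 40 that is treated for 8 days. Under the wording of 7.4 this subject leaves the PP Week 4 ANCOVA (Table 14.2.2.2) and the PP results for Weeks 1 to 3 as well. A subject who simply drops out after Visit 4 still meets the visit requirement of 7.2.5 and is not removed on that ground.

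At stake is whether PP can do its supporting job. It could agree or disagree with mITT for reasons unrelated to the Week 4 effect.

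**Working it through.** The plan states no figure on this point, so there is none to reproduce. The core of the check is a comparison of dates.

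**1. Endpoint window.** Under SAP 6.5.3, Week 4 WI-NRS uses diary days from Day 22 to the earlier of Day 28 and the day before Visit 4.

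**2. Exclusion window.** Under SAP 7.5.4 and Listing 16.2.13.3, follow-up rescue days run from the day of Visit 4 to the day before Visit 5.

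**3. Overlap.** There is none for the diary endpoints: the first window closes by Visit 4 - 1 and the second opens at Visit 4. IGA, EASI, POEM and 5-D are assessed at Visit 4 itself, so for these an event earlier on that day could still matter.

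**4. Reach.** The PP repeat of the primary ANCOVA (Table 14.2.2.2) includes everyone who meets PP criteria. No Week 4 version of PP is defined.

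**5. The plan's own comparison.** The Sub-Analysis and the non-responder imputation in SAP 7.4 are triggered by on-treatment rescue only, which ends at Visit 4 - 1 (SAP 6.5.6). The Sub-Analysis keeps data from before the event. Time order is respected there but not in the PP flag.

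**6. Size, on assumed inputs.** Let f be the share newly excluded in an arm and d the Week 4 gap between excluded and kept subjects, taken as equal in both arms. Positive d means the excluded did worse.

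- Mean of kept = mean of all - f × d.
- Benefit over vehicle among kept = benefit among all - (f_vehicle - f_B244) × d.
- Example, 15% v 8% excluded and d = 1.5: 0.07 × 1.5 = 0.105, a loss of 0.105/0.65 = 16% of the planned difference.
- Range, a differential of 3 to 10 percentage points and d of 1 to 2: 0.03 × 1 = 0.03 to 0.10 × 2 = 0.20, or 5% to 31% of 0.65. The sign reverses if B244 loses more subjects than vehicle.

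**7. Simulation, also on assumed inputs.** There were 2,000,000 subjects per arm, with changes normal with SD 2.5 (SAP 7.1) and a vehicle mean of -2 (assumed). Vehicle exclusion was set at 5%, 10% or 20%. The log-odds of removal rose by 0.2 or 0.4 per point of worse Week 4 change, with an added log-odds for B244 of 0 or 0.7.

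| True benefit | Removal depends on Week 4 change only | Added log-odds 0.7 for B244 |
|---|---|---|
| 0 | about 0 | 0.06 to 0.22 |
| 0.65 | 0.58 to 0.64 | 0.69 to 0.79 |

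The formula agrees with this. In the mildest no-effect case with the added log-odds, vehicle shifted by 0.061 with 5% excluded, so d = 0.061/0.05 = 1.22. B244 lost 9.5%, so the predicted false benefit is (0.095 - 0.05) × 1.22 = 0.055, against 0.056 simulated.

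**The case against.** Several points on the other side stand.

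- **It is tempting to say that 7.4 contradicts 7.2.5.** The documents do not support that. The test in 7.2.5 concerns the efficacy assessments in general, and the same PP set serves WI-NRS and AI-NRS in Weeks 1 to 8 and the clinic scales at Weeks 2, 4 and 8. Heavy rescue in follow-up clearly matters for Weeks 5 to 8. The weakness is one set serving endpoints with different windows.
- **It is tempting to treat removal as certain.** SAP 7.4 says that such subjects are excluded, but 7.3.2 says only that they may be, at the sponsor's discretion and before unblinding. Deviations are graded under a guidance document that is not part of the plan. Blinded review prevents picking by arm, but it does not prevent selection on a post-endpoint outcome.
- **The trial's main conclusion does not depend on it.** The mITT analysis, its rescue-based variants, and the addendum's worst-observation (mITT) and last-observation (ITT) analyses do not use the PP filter.
- **The illustration may overstate the size.** Some subjects over the follow-up limit may already be out of PP for washout, treatment or other deviations. Only the additional exclusions count.
- **PP stays imperfect after any fix.** It would still be selected on on-treatment rescue, which is also post-randomisation.

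None of this answers the timing point: no section stops a follow-up event from removing a subject from the Week 4 PP analysis.

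**Conclusion.** The point holds for a supportive analysis. As written, SAP 7.4 lets events after Visit 4 decide who enters the PP analyses of Weeks 1 to 4. This is explicit for rescue over the follow-up limit, follows from the whole-study wording for excluded medications, and is inferred for antihistamine and emollient changes.

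The illustrative shift of about 0.03 to 0.20 points rests wholly on assumed exclusion rates and gaps. A reader might infer that the rule favours B244. The documents do not show that: when removal depends only on the Week 4 outcome, the simulated difference is unchanged under no effect and slightly diluted under a true 0.65. A false benefit appears only with an added, assumed arm effect on follow-up rescue. The change is worth making because it is cheap and PP is the named support for mITT, but the definitive result is not in doubt on this account.

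**What to change.** In SAP 7.2.5 and 7.4, for PP analyses of Week 1 to 4 endpoints, count confounding events only up to the end of the endpoint's window:

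- diary WI-NRS and AI-NRS: through Visit 4 - 1;
- IGA, EASI, POEM and 5-D: through the Visit 4 assessment.

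Apply later events only to the PP data of Weeks 5 to 8, for example by dropping those subjects' Week 5 to 8 data. State dates for the antihistamine and emollient items. Reconcile 7.2.5, 7.3.2 (removal possible) and 7.4 (removal stated) so that one rule governs the flag. The rescue limits are not part of this point and stay unchanged.

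The cost is a short text change and a date condition in the PP flag, with no new data. The downside is that the PP count will differ between the Week 4 and Week 8 tables, which a footnote can explain.

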7.4.1 Analysis of WI-NRS and AI-NRS

The primary endpoint of mean change from Baseline to Week 4 in WI-NRS will be analyzed using analysis of covariance (ANCOVA) models.

In addition, the continuous efficacy endpoints WI-NRS, AI-NRS will be summarized using descriptive statistics at Baseline, Week 1, Week 2, Week 3, Week 4, Week 5, Week 6, Week 7, and Week 8 for actual values and change from Baseline values.

The difference in treatment groups in change from Baseline values at post-baseline visits will be analyzed using a mixed model with repeated measures to account for within subject variability and including visit (Baseline vs. Week 1, Week 2, Week 3, Week 4, Week 5, Week 6, Week 7, Week 8), treatment group, visit-by-treatment interaction, and Baseline value as explanatory variables. The subject variability will be modelled using a compound symmetry covariance matrix. Other types of covariance structure may be applied should they provide a better model fit.

The frequency and rate of WI-NRS and AI-NRS responders at Week 1, Week 2, Week 3, Week 4, Week 5, Week 6, Week 7, Week 8 (\geq 4 point change from Baseline in WI-NRS and AI-NRS) and other responder endpoints (any improvement from Baseline in WI-NRS and AI-NRS, defined as \geq 1 point change from Baseline) will be reported and compared between treatment groups using a logistic regression model by week. Generalized estimating equations to account for repeated measures and within-subject variability may also be applied. Responder status varies by outcome measure, endpoint, and visit. That is, a subject can be considered a responder at one visit, but not the next for a specific measure. Similarly, a subject can be considered a responder for one measure but not another at the same visit.

Additionally, daily WI-NRS and AI-NRS scores will be presented in by-subject data listings.

7.4.2 Analysis of Primary Endpoint of Change from Baseline to Week 4 in Weekly Average WI-NRS

The ANCOVA model for the primary endpoint change from Baseline to Week 4 in weekly average WI-NRS will have treatment group and Baseline weekly average WI-NRS as explanatory variables. Hypothesis testing will be done using a Dunnett Testing Method, applying pairwise comparisons of each respective B244 dose group to vehicle using a one-sided familywise error rate of 0.10. Treatment effect will be estimated as least squares means using vehicle as reference and adjusted for multiplicity according to the Dunnett Testing Method and presented with one-sided 90% CI.

Additionally, the two B244 dose groups will be compared by presenting the treatment difference estimated using least squares means.

Finally, in a separate analysis, the pooled B244 dose groups will be compared to vehicle using the same ANCOVA model.

STATISTICAL ANALYSIS PLAN

Version 3.0 12-Jan-22

